8.1.3 Measurement Methods

All measurements should be recorded in metric notation (i.e., decimal fractions of centimeters) using a ruler or calipers. The same method of assessment and the same technique must be used to characterize each identified and reported lesion at baseline and during follow-up. For patients having only lesions measuring at least 1 cm to less than 2 cm must use CT imaging for both pre- and post-treatment tumor assessments.

Imaging-based evaluation is preferred to evaluation by clinical examination when both

methods have been used at the same evaluation to assess the antitumor effect of a treatment.

8.1.3.1 Target Lesions

All measurable lesions up to a maximum of 2 lesions/organ and 5 lesions in total, representative of all involved organs/tissues should be identified as target lesions.

8.1.3.2 Non-Target Lesions

All non-measurable lesions and measurable lesions that have not been selected as target lesions should be included as non-target lesions.

The primary lesion should always be classified as a non-target lesion irrespective of its size and whether or not it can be accurately measured.

Lymph nodes that have a short axis <10 mm are considered non-pathological and should not be recorded.

Any equivocal lesion without clear diagnosis (eg, uncharacteristic solitary lung nodule without biopsy, uncharacteristic thyroid mass lesion without fine needle aspiration) may be considered a non-target lesion if it cannot be differentiated from a benign lesion.

All other lesions (or sites of disease), including pathological lymph nodes, should be identified as non-target lesions and should also be recorded at Baseline. Measurements are not required, but their presence, absence, or unequivocal progression should be followed throughout the study.

It is possible to record multiple non-target lesions involving the same organ as a single item on the CRF (eg, multiple enlarged pelvic lymph nodes or multiple liver metastases).

8.1.4 Response Definition

A sum of the longest diameter for all target lesions plus the sum of the short axis of all the target lymph nodes will be calculated and reported as the baseline sum of dimensions (BSD). The BSD will be used as reference to further characterize any objective tumor response in the measurable dimension of the disease.

On follow up imaging a sum of the longest diameter for all target lesions plus the sum of the short axis of all the target lymph nodes will be calculated and reported as the post-baseline sum of dimensions (PBSD). If the radiologist is able to provide an actual measure for the target lesion (or target lymph node), that should be recorded, even if it is below 0.5 cm. If the target lesion (or target lymph node) is believed to be present and is faintly seen but too small to measure, a default value of 0.5 cm should be assigned. If it is the opinion of the radiologist that the target lesion or target lymph node has likely disappeared, the measurement should be recorded as 0 cm.

Response categories	Definition	Comment
Complete Response (CR)	The disappearance of all target lesions. Any pathological lymph nodes must have reduction in short axis to <10 mm.	Requires normalization of tumor markers. All lymph-nodes must be non-pathological in size (<10mm short axis).

		Persistence of one or more non-target lesion(s) and/or maintenance of tumor marker level above the normal limits is considered PR or SD depending on the baseline.
Partial Response (PR)	At least a 30% decrease in the sum of diameters of the target lesions, taking as a reference the baseline sum diameters.	
Stable Disease (SD)	Neither sufficient shrinkage to qualify for PR nor sufficient increase to qualify for PD, taking as a reference the smallest sum diameters while on study.	
Progressive Disease (PD)	At least a 20% increase in the sum of diameters of the target lesions, taking as a reference the smallest sum on study, including the baseline sum. In addition to the relative increase of 20%, the sum must also demonstrate an absolute increase of at least 5 mm. Definitive new lesion presence also indicates progression.	Unequivocal progression of existing non-target lesions with below definition is considered PD. There must be an overall level of substantial worsening in non-target disease such that, even in the presence of SD or PR in target disease, the overall tumor burden has increased sufficiently to merit discontinuation of therapy.

Because worsening in non-target disease cannot be easily quantified, a useful test that can be applied when assessing patients for unequivocal progression is to consider if the increase in overall disease burden based on the change in non-measurable disease is comparable in magnitude to the increase that would be required to declare progressive disease (PD) for measurable disease; ie, an increase in tumor burden representing an additional 73% increase in ‘volume’ (which is equivalent to a 20% increase diameter in a measurable lesion).

8.2 Treatment Beyond Progression

Subjects will be permitted to continue with treatment beyond initial RECIST 1.1 defined progressive disease as long as they meet the following criteria:

- Investigator-assessed clinical benefit
- Subject is tolerating treatment
- Treatment beyond progression will not delay an imminent intervention to prevent serious complications of disease progression (e.g., CNS metastases)

The assessment of clinical benefit should take into account whether the subject is clinically deteriorating and unlikely to receive further benefit from continued treatment. If the decision is taken to continue treatment beyond progression, the subject will remain on the trial and continue to be treated and monitored according to the study calendar.

Subjects should discontinue treatment upon further evidence of further progression (second progression), defined as an additional 20% or greater increase in tumor burden (SPD: sum of product of diameters) from time of initial progression (including all target lesions and new measurable lesions). New lesions are considered measurable at the time of initial progression if the longest diameter is at least 10 mm (except for pathological lymph nodes, which must have a short axis of at least 15 mm). Any new lesion considered non-measurable at the time of initial progression may become measurable and therefore included in the tumor burden measurement if the longest diameter increases to at least 10 mm (except for pathological lymph nodes, which must have an increase in short axis to at least 15 mm). Treatment should be discontinued permanently upon documentation of further progression.

9. Correlative Studies

We propose a series of assays to help us identify the predictive biomarkers for future clinical trials. Efforts should be made for all patients with biopsiable lesion to undergo biopsy on day #11-19. The archival tissue and biopsied tissue will be banked for future analysis. Biopsy is planned to assess changes in the immune microenvironment due to regorafenib.

Additionally, all subjects will have liquid biopsies at baseline and with the first restaging and then at progression (if different than the first restaging).

The discovery of biomarkers relevant to the field is expanding rapidly and thus the list of biomarkers will be assessed at the time of analysis. A panel of biomarkers of interest are listed below.

Tissue:

- Expression of PDL1. PD-1 expression in tumor tissue.³³ MHC class I and II expression at baseline (archival tissue) and in collaboration with Merck.
- Additionally, archival tumor tissue will be obtained for NGS and correlation between CMS classification, mutational load, and immune scoring and treatment benefit.

Blood:

- A panel of proprietary biomarkers (SNPs in angiogenic and immune pathways) developed at [name] lab will be used for assessment of toxicity and efficacy.
- We intend to look at the global markers of immune activation by screening PBMC for: CD3, CD4, CD8, CD25, FoxP3, HLA-DR, ICOS1, CTLA-4, CD45RO, CD45RA, CD27, PD-1, CCR7, CD 62L, CD 69, ICOS, CD 95, CD127 and CD137 for analysis

by multi-color flow cytometry to phenotype and quantify the changes in immune markers following treatment on both CD4⁺ helper T cells, regulatory T cells and CD8⁺ cytotoxic T cells. Specifically the following sets of antibodies will be informative to the function of the T cells: CD45RA/CCR7/CD62L (naïve vs memory), FoxP3/CD25/CD127/CTLA-4 (nTreg), CD69/ICOS/PD-1/CD95 (activation vs exhaustion).

- Additionally, will collect CTC, cell free RNA and DNA at baseline and at progression for analysis of expression of MHC class I and II expression, and mutational load.

10. Statistical methods and determination of sample size

This is an open label single institution phase I/II with combination of regorafenib and pembrolizumab in patients with advanced colorectal cancer who have progressed or not tolerated standard therapies.

End points:

- Phase I: Dose limiting toxicity during the first course of therapy.
- Phase II: Progression-free survival (PFS), defined from the start of treatment (day 1 of cycle 1) to the time of disease progression or death from any cause whichever is sooner. Patients will be considered evaluable for PFS if they have received at least one dose of treatment and have at least one post baseline tumor assessment.
- Phase II: Overall survival, defined as the time from the start of treatment (day 1 of cycle 1) to death from any cause.

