7.4 Appropriateness of procedures / measurements

The assessments described in the previous sections are widely used and generally recognized as reliable, accurate, and relevant for determining the safety and efficacy of therapies in this

disease.

8. Treatment Evaluation Using RECIST Guideline

Response and progression will be evaluated in this study using the international criteria proposed by the revised Response Evaluation Criteria in Solid Tumors (RECIST) guidelines (version 1.1) (Eisenhauer, et al, 2009). Changes in the largest diameter (unidimensional measurement) of the tumor lesions and the short axis measurements in the case of lymph nodes are used in the RECIST guideline.

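### The second-progression stopping rule in section 8.2 is set on a sum of products of diameters, but sections 8 and 8.1.4 record one dimension per lesion, and 20% is not the same threshold on the two scales

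*Combined protocol and SAP*

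**What the plan says.** Section 8.2 permits treatment beyond a first RECIST 1.1 progression under stated conditions. It then defines second progression as an "additional 20% or greater increase in tumor burden (SPD: sum of product of diameters", counted "from time of initial progression (including all target lesions and new measurable lesions". The consequence is firm: "Treatment should be discontinued permanently upon documentation of further progression".

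The measurement system described before that is one-dimensional. The opening of section 8 says "Changes in the largest diameter (unidimensional measurement) of the tumor lesions and the short axis measurements in the case of lymph nodes are used". Section 8.1.4 builds the baseline and post-baseline sums the same way: at follow-up the "sum of the longest diameter for all target lesions plus the sum of the short axis of all the target lymph nodes will be calculated". First progression in section 8.1.4 is "At least a 20% increase in the sum of diameters of the target lesions, taking as a reference the smallest sum on study", together with an absolute rise of 5 mm or more.

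The sum of products appears only in section 8.2. Sections 8 to 8.1.4 nowhere ask for a perpendicular diameter. Section 8.2 itself admits new lesions on a single dimension: 10 mm in longest diameter, or 15 mm in short axis for nodes.

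**The concern.** A product of diameters needs two measurements per lesion, and the plan specifies one. Someone applying section 8.2 must either take a second diameter that the plan does not ask for, or apply the 20% to the sum of diameters instead. These are different rules. The number 20% appears in both section 8.1.4 and section 8.2, which invites the reader to treat the thresholds as equivalent.

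At stake is when patients treated beyond progression must stop, and whether that decision is made the same way for every patient. Section 3 foresees one or two further institutions, although section 10 calls the study single-institution.

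**Working it through.** **Inputs.** From section 8.2: 20% in the sum of products (SPD), with no absolute minimum. From section 8.1.4: 20% in the sum of diameters and at least 5 mm, and a statement that 20% in diameter equals 73% in volume. From sections 6.2 and 7: scans every 8 weeks, with a seven-day window in the section 7 calendar. From section 4: tolerability judged against a rise from 1.7 to 2.0 months.

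**1. The plan's own conversion.** If every dimension grows by a fraction g, volume grows by (1 + g)³ − 1. With g = 0.20, 1.20³ − 1 = 0.728, which rounds to the stated 73%. The plan therefore assumes proportional growth when it moves between dimensions.

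**2. The same assumption applied to SPD.** SPD grows by (1 + g)² − 1.
- 20% in diameter: 1.20² − 1 = 44% in SPD.
- 20% in SPD: g = √1.20 − 1 = 0.0954, about 9.5% in diameter.

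**3. Other growth patterns, one lesion.** Suppose the perpendicular diameter grows c times as fast as the longest. Solve (1 + g)(1 + c·g) = 1.20 for g, the growth in longest diameter that triggers the rule. The values of c are assumptions.

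| c | g |
|---|---|
| 0 | 20.0% |
| 0.5 | 12.8% |
| 1 | 9.5% |
| 2 | 6.4% |

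**4. Several lesions, one growing.** Assume round lesions, so that SPD is the sum of squared diameters, and let one lesion of diameter d grow until SPD is up 20%. Its new diameter is √(d² + 0.2·SPD).
- Lesions of 50, 30 and 20 mm: SPD = 2500 + 900 + 400 = 3800, and 0.2 × 3800 = 760. If the 50 mm lesion grows, √3260 − 50 = 7.1 mm, or 7.1% of the 100 mm sum. If the 20 mm lesion grows, √1160 − 20 = 14.1 mm, or 14.1%.
- Lesions of 60, 15, 15 and 10 mm: 6.6% if the largest grows, 20.5% if the smallest grows.

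SPD is thus usually, but not always, the tighter scale.

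**5. Opposite decisions from one scan.** With 12% proportional growth since initial progression, 1.12² − 1 = 25.4% in SPD, so treatment stops. On the sum of diameters 12% is below 20%, so treatment continues. Under proportional growth the scales disagree from 9.5% up to 20% in diameter.

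**6. The absolute minimum.** At 9.54% growth the rise is below 5 mm whenever the sum at initial progression is under 5 / 0.0954 = 52.4 mm. On a 30 mm sum it is 30 × 0.0954 = 2.9 mm.

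**7. When the rule can act.** It needs a first progression (week 8 at the first scheduled scan) and a later scan (week 16). That is 112 / 30.44 = 3.7 months, or 105 / 30.44 = 3.4 months if the second scan is taken a week early.

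**The case against.** The strongest reply is that little turns on this. Most of that reply stands.

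- **PFS.** A reader might infer that the primary endpoint is affected. It is not: section 10.5 fixes the PFS event at initial RECIST 1.1 progression or death, so the PFS test and the 63 patients do not depend on section 8.2.
- **Tolerability.** Section 7.2 defines tolerability as median duration of combination therapy, so a reader might infer that the stopping rule biases that verdict. The scan schedule does not support this. A patient stopped by the rule on scheduled scans has passed about 3.4 months, well beyond the 2.0-month mark. The rule could move the estimated median only if that median were already beyond about 3.4 months, when the criterion is met anyway. Unscheduled early scans are the exception. Individual durations can still change.
- **The 9.5%.** It is not a fixed conversion. It needs proportional growth, and if the perpendicular diameter does not grow there is no tightening at all.
- **Tighter than first progression.** The two rules also differ in reference point (smallest sum on study against initial progression) and in lesions counted (new measurable lesions enter only the second sum). A different threshold for a different decision can be a deliberate choice, and so can omitting the 5 mm minimum. The documents do not show that either is a mistake.
- **Impossible to apply.** This goes too far. The case report forms are not in the documents, and section 11.2.5 says images are stored at USC, so a second diameter could be read from them. The supportable statement is narrower: SPD cannot be derived from the sums the plan specifies, and no section asks for the extra measurement.

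The reply does not remove the contradiction between section 8.2 and sections 8 and 8.1.4 on what is measured.

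**Conclusion.** The concern holds as an internal inconsistency in a mandatory stopping rule. The measure in section 8.2 cannot be computed from the one-dimensional sums in section 8.1.4, and the shared 20% is a different threshold on each scale. The size is about 9.5% in diameter under proportional growth, the assumption behind the plan's own 73%. For a single lesion it is roughly 6% to 20% when the perpendicular diameter grows between zero and two times as fast as the longest.

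The practical consequence is confined to patients treated beyond progression, for whom the same scan can lead to stopping or continuing depending on the scale used. The documents do not say how many such patients to expect. No error in the primary inference follows, and a changed 2.0-month tolerability decision is unlikely on the planned scan schedule. Nor do the documents show which scale was intended, so this point does not favour either one.

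**What to change.** Reconcile the opening of section 8, section 8.1.4 and section 8.2 so that these items all use one scale:
- the measure that defines second progression;
- its percentage threshold on that measure;
- whether an absolute minimum applies;
- the dimensions to be recorded for target lesions, nodes and the new lesions that section 8.2 already admits.

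The sponsor decides which measure and threshold apply.

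The cost is a short text change. If the sponsor keeps the sum of products, add a second diameter per lesion, read from existing scans, and a place to record it. If a one-dimensional measure is chosen, no further dimension per lesion is needed.

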10.1 Study design/sample size calculation

A standard 3+3 dose escalation rule will be used during the phase I portion of the study to determine MTD/RP2D of combination of regorafenib and pembrolizumab. 3 dose levels of regorafenib will be assessed. The dose level of pembrolizumab will be fixed. The definitions of DLTs, MTDs, and DLT observation period as well as rules for dose escalation, expansion, and de-escalation are clearly defined in section 6. The study could be stopped when ≥ 2 out of the first 3 patients treated at starting dose experienced DLTs. Or all dose levels are expanded with additional 3 patients. Thus 3 to 18 patients could be enrolled and treated during phase I part of the study.

As soon as MTD/RP2D is determined, the phase II portion of the study will start. We use SWOG's one arm non-parametric survival design to determine the sample size. Progression-free survival will be the primary endpoint. PFS is defined from the start of treatment (day 1 of cycle 1) to the first observation of disease progression or death whichever comes first. The patients are alive and disease progression is not observed, PFS is censored at the date of the latest disease assessment. 63 patients are planned to enroll to have 80% power to detect improvement of median PFS from 1.9 months (CORRECT trial, the historical control, the null hypothesis) to 2.85 months (the alternative hypothesis). The type I error rate using this design will be 0.1 (one sided). The planned accrual time is 2 years and the additional follow-

up time from the end of accrual is 6 months. An expected 20 events are expected to occur during the follow up period.

The approximate upper critical PFS value is 2.44 months.

The total sample size of this phase I/II study is between 3 and 75 patients. Six patients who are treated at MTD/RP2D of the phase I portion of the study will be counted for the phase II portion of the study too.

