We propose to combine regorafenib and PD1 (pembrolizumab) in colorectal cancer patients in 3rd and 4th line setting. Using a phase I/II design, we will first enroll 3-18 patient on phase I to find the recommended dose for phase II. We will then accrue patients to the phase II portion of the trial with the primary efficacy endpoint of PFS. An extensive biomarker analysis, liquid biopsies and tumor tissue, is planned to identify the population who would most benefit from this combination.

Four patients on dose level 1: 80mg were reviewed by the Phase I DLT Committee. One patient was deemed inevaluable for DLT and was replaced. Three patients were evaluable with no DLT. The trial was recommended to proceed to accrue three patients to dose level 2: 120mg. All three patients at this dose level had either grade 2 or grade 3 rash which required a dose reduction at either cycle 2 or 3. It was determined that the dose level 2: 120mg would

be challenging due to its overall tolerability; therefore, dose level 1: 80mg was recommended to expand and enroll additional three patients for a total of 6 patients to be reviewed.

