5.2.3 Replacement

During phase I, for subject who dropout due to reasons other than toxicity, we will replace that subject with another subject. These subjects will be followed for PFS.

6. Treatment[s]

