10.2 Analysis sets

During the phase I portion of the study. All patients who are evaluable for DLTs will be counted and used in the decision of dose escalation, expansion, de-escalation, and stopping. Patients who are inevaluable for DLTs will be replaced. However, all eligible patients who start treatment with study drugs will be counted in patient description. During the phase II portion of the study, all patients who start treatment with study drugs will be included. All patients need scan at the end of their study period to be counted for endpoints.

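### The phase I carry-over rule counts six patients at the recommended dose, but the protocol lists seven at 80 mg and does not say which six enter the PFS set

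*Combined protocol and SAP*

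**What the plan says.** **Carry-over rule.** Section 10.1, and the subject-number row of the synopsis, admit phase I patients to phase II as follows: "Six patients who are treated at MTD/RP2D of the phase I portion of the study will be counted".

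**Patients at 80 mg so far.** Section 1.1 reports: "Four patients on dose level 1: 80mg were reviewed by the Phase I DLT Committee". It continues: "One patient was deemed inevaluable for DLT and was replaced". Then: "Three patients were evaluable with no DLT". After the 120 mg cohort, "dose level 1: 80mg was recommended to expand and enroll additional three patients for a total of 6 patients to be reviewed". No reason is given for the inevaluability, and the treatment that patient received is not stated.

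**Replacement.** Section 5.2.3 says: "During phase I, for subject who dropout due to reasons other than toxicity, we will replace that subject with another subject". Its next sentence provides for PFS follow-up, without making clear whether that means the dropouts or their replacements.

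**Analysis set.** For phase II, section 10.2 says that "all patients who start treatment with study drugs will be included", then adds that a scan at the end of the study period is needed to count for endpoints. The endpoint list at the start of section 10 makes PFS evaluability depend on one dose and at least one post-baseline tumor assessment.

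**The concern.** Six is a toxicity number. The MTD definition in section 6.2 needs at least six patients treated and evaluable for toxicity, and the expansion at 80 mg is sized to reach that. Replacing inevaluable patients is proper for a DLT decision. It is not a sound basis for choosing who enters a time-to-event efficacy analysis.

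DLT evaluability is judged over the first 21-day cycle, and non-toxicity dropouts, who are replaced, can include patients with early progression or decline. If the carry-over group is the DLT-evaluable group, its members are partly selected by what happened after treatment began, while patients entering phase II directly are included once they start treatment. The comparison is with a fixed historical median of 1.9 months, so such selection would tend to favour the combination. If the six are instead chosen in some other way, the choice is unspecified in a trial where outcomes are visible.

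**Working it through.** **1. Count at 80 mg (section 1.1).**
- Listed: 4 + 3 = 7.
- DLT-evaluable: 3 + 3 = 6, assuming no further replacement in the expansion.
- Carried over (10.1, synopsis): 6, which equals the evaluable count and is one fewer than the listed count.
- The stated maximum of 75 fits the same six: 18 + 63 − 6 = 75. With seven carried over it would be 18 + 63 − 7 = 74, or 19 + 63 − 7 = 75 if the replaced patient is added to the phase I maximum.

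**2. The plan's own sample size.** Inputs from 10.1: medians 1.9 and 2.85 months, one-sided alpha 0.10, power 80%. Test survival at 1.9 months, without censoring: S0 = 0.50 and S1 = 0.5^(1.9/2.85) = 0.630.
- Log(−log) variance: N = {[1.2816/ln 2 + 0.8416 × √(0.370/0.630)/(−ln 0.630)] / ln 1.5}² = 64.04.
- Binomial variance: N = {[1.2816 × 0.5 + 0.8416 × √(0.630 × 0.370)] / 0.130}² = 64.92.

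Both are within two patients of the stated 63; power at 63 is 79.6% and 79.1%. Moving one patient in or out changes power by about 0.5 points (log(−log): 79.1% at 62, 80.0% at 64). Precision is therefore not the issue; selection is.

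**3. Upper bound on type I error.** Assume exponential PFS with median 1.9 months. Twenty-one days is 0.69 months, so the chance of an event by then is 1 − exp(−ln 2 × 0.69/1.9) = 0.22. Simulate 63 patients, reject when the observed median exceeds a cut-off, and set the cut-off to give 10% under the null. Then condition some patients on 21 event-free days:

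| Patients conditioned | Type I error |
|---|---|
| None | 10.0% |
| One of 63 | 10.6% |
| Six of 63 | 13.6% |

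**4. Lower early hazard.** Scans are every 8 weeks, so a PFS event before day 21 would almost always be a death or clinical progression, and 22% is probably too high. Keep the 1.9-month median, and assume that only 2%, 5% or 10% have an event by day 21 (my range; the documents give no figure). Conditioning all six then gives about 10.2%, 10.7% and 11.3%.

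**5. The one known patient.** At the same cut-off, leaving the patient out gives the nominal 10%. Counting the patient as an early failure (n = 64) gives about 8%. The 8% depends wholly on assuming an early failure.

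**The case against.** A reader might infer that an early failure has been removed from the primary analysis and that the carried-over six have guaranteed event-free time. The documents do not support that.

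- No section says the replaced patient is excluded from PFS. The count of six sits in the sample-size section and serves the planning total. Section 10.2 governs analysis sets and includes all who start treatment, section 7.2 measures PFS in subjects who start treatment, and section 5.2.3 provides for PFS follow-up. These lean towards inclusion.
- Section 1.1 says only that the patient was inevaluable for DLT. It does not say that the patient dropped out, progressed or died, or how much drug was given.
- Section 1.1 recommends expanding 80 mg; it does not declare it the recommended dose.
- DLT-evaluable does not mean progression-free. A patient with a DLT is evaluable, and section 8.2 allows treatment beyond progression.
- Constant hazard fits poorly. Section 1.4.2 gives CORRECT medians of 1.9 and 1.7 months with a hazard ratio of 0.494; exponential curves would imply 1.7/0.494 = 3.4 months on regorafenib.
- The assessment and scan conditions in sections 10 and 10.2 could exclude the same patient whatever the count of six means.

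All of this stands, and it limits the size of the point and the confidence in its direction. It does not remove the mismatch. The all-treated rule in 10.2 is written for the phase II portion, and the only text admitting phase I patients to that portion says six. With seven listed, someone is left out or the choice is open.

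**Conclusion.** The point holds as a gap in the definition of the primary analysis set, not as a demonstrated bias. It rests on two conditions that the documents do not settle: that 80 mg becomes the recommended dose, and that the seventh patient received study drug.

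The likely effect on the one-sided error is small: about 10% to 11% with one patient conditioned or with a lower early hazard, against a nominal 10%. The 13.6% is an upper bound, because it needs all six conditioned and a constant hazard, while only one replacement is documented. Further replacements in the three-patient expansion would widen the gap between treated and counted. It is worth correcting because it concerns the primary endpoint and the correction is simple.

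**What to change.** In section 10.1 and the synopsis, replace the count of six with: all phase I patients who received at least one dose of study treatment at the dose selected as RD, including any replaced for DLT evaluation. State that DLT evaluability is used for the escalation decision only, and bring the total of 75 into line.

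In the same edit, reconcile the post-baseline assessment condition (start of section 10) and the end-of-study scan condition (10.2) with the all-treated set. Clinical progression or death before the first scan should count as a PFS event, and patients with no event and no scan should be censored, not removed. Without this, the new carry-over wording may not bring the replaced patient in.

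The cost is a few sentences. No treatment changes, and section 5.2.3 already provides for PFS follow-up, though it should say whose. The downside is that the PFS estimate may become slightly less favourable.
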